**1.4 Initial Clinical Data**

CART-19 cells with a 4-1BB:TCR $\zeta$  have not been previously tested in humans; however a recent report testing CART-20 cells with a TCR $\zeta$  reported safety in patients with mantle cell lymphoma. Results from related approaches testing T bodies / CARs in humans are available from

CONFIDENTIAL

This material is the property of Children's Hospital and the University of Pennsylvania. Do not disclose or use except as authorized in writing by the study sponsor

patients with HIV infection and cancer. Human data relevant to CART-19 cells is summarized below:

CD4:TCR $\zeta$  experience in HIV infection. CD4 $\zeta$  is a genetically engineered, MHC–unrestricted receptor composed of the  $\zeta$  subunit of the CD3 T cell receptor, the cytoplasmic domain involved in signal transduction, fused to the transmembrane and extracellular domains of human CD4, which targets HIV *env* expressed on the surface of infected cells. Upon binding to HIV envelope, CD8+ T cells engineered to express the CD4 $\zeta$  fusion protein proliferate and initiate effector functions such as cytokine secretion and HIV-specific cytolytic activity. In collaboration with [name] at Cell Genesys Inc. and others, we assessed the survival of co-stimulated gene–marked T cells in 3 published studies. CD4 $\zeta$  modified T cells were detected by DNA PCR in the peripheral blood of all patients following infusion, and sustained mean levels of 1 to 3% of T cells were detected at all time points after infusion. In extended follow-up, CD4 $\zeta$  was detected in the blood of 17 of 18 patients 1 year following infusion. In the only published phase II HIV gene therapy trial, 40 patients were randomized to receive an infusion of CD4 $\zeta$ –modified T cells or non-transduced costimulated T cells; the treatment was found to be safe and associated with treatment-related increases in CD4 T cell counts. Together these clinical results indicate that CD4 $\zeta$  CAR anti-HIV vector is safe and has stable engraftment and persistence in lymphopenic patients with HIV infection.

G250:TCR $\zeta$  experience in renal cell carcinoma. Lamers and colleagues recently reported the interim results of a trial testing T bodies in 3 patients with metastatic renal cell carcinoma. The T bodies were targeted with an scFv specific for carboxy-anhydrase-IX (the G250 antigen) that is overexpressed on clear cell RCC and in the biliary tract. The T body was expressed in autologous T cells using retroviral transduction. The subjects were treated with a dose-escalation scheme of intravenous doses of  $2 \times 10^7$  T cells at day 1;  $2 \times 10^8$  T cells at day 2;  $2 \times 10^9$  T cells at days 3 through 5 (treatment cycle 1); and  $2 \times 10^9$  cells at days 17 to 19, in combination with human recombinant IL-2, given subcutaneously at  $5 \times 10^5$  U/m^2 twice daily administered at days 1 to 10 and days 17 to 26. Infusions of these G250 T bodies were initially well-tolerated. However, after four to five infusions, liver enzyme disturbances reaching NCI CTC grades 2 to 4 developed. These toxicities necessitated the cessation of treatment in subjects 1 and 3, corticosteroid treatment in patient 1, and reduction of the maximal T-cell dose in subjects 2 and 3. All three patients developed low levels of anti-scFv (G250) antibodies between 37 and 100 days after the start of T-cell therapy. The liver enzyme elevations resolved. The T bodies circulated from 32 to 53 days after infusion, and the authors could demonstrate anti-tumor activity of the G250 T body cells in the peripheral blood of the patients after infusion. The authors concluded that the liver toxicity was most likely due to the reactivity of G250 T bodies against the target antigen expressed on normal tissue, that is, the epithelial cells lining the bile ducts. Thus, this is interpreted as a form of “on target, off organ” toxicity.

Anti-CD20 expressing CD8 cells for follicular lymphoma. Jensen, Press and colleagues reported a clinical trial evaluating escalating doses of CD8 T cells modified by electroporation to express a chimeric immune receptor targeting the CD20 B cell marker and linked to the CD3zeta activation domain for the treatment of refractory follicular lymphoma and mantle cell lymphomas. A total of 7 subjects were enrolled in the trial, and each received 3 infusions of escalating doses of CD20 specific CARTs of  $10^8$  cell/m^2,  $10^9$  cell/m^2, and  $3.3 \times 10^9$  cell/m^2 spaced 2 to 5 days apart. The first three patients had poor persistence of the cells post infusion, which was improved in the last 4 patients who received subcutaneous low dose (500,000 IU/m^2)

CONFIDENTIAL

IL-2 twice daily for 14 days. No subjects developed an immune response to the infused cells, which was evaluated by chromium release assay against targets expressing the scFv and neomycin resistance gene products (for cellular immunity), and by ELISA for antibody responses to the anti-CD20 antibody. Two patients became positive for HAMA 3 and 6 months after infusion. Since the chimeric immune receptor does not contain the murine Fc region, the conversion to HAMA positivity may reflect immune reconstitution and response to prior therapy. Clinical responses were modest, with no grade 3 or 4 toxicities. Toxicities were restricted to the four patients receiving IL-2, and were attributed to an IL-2 induced flu like syndrome.

Folate Receptor-Fcγ expressing T cells for ovarian cancer. Kershaw, Hwu and colleagues carried out a 14 patient trial with two cohorts evaluating a CIR targeting the folate receptor and linked to the Fcγ signaling chain109b. This trial consisted of two cohorts, the first of which received three cycles of escalating doses of T bodies expanded with antiCD3 Ab and IL-2 for doses of  $3 \times 10^9$ ,  $1 \times 10^{10}$  and  $3-5 \times 10^{10}$  respectively, combined with systemic IL-2. The second cohort received 1-2 cycles (depending upon the number of cells available) of cells expanded with allogeneic PBMCs and IL-2, followed by allogeneic stimulation in vivo with live unirradiated PBMCs. Doses ranged from  $4-169 \times 10^9$  cells, and two of six patients received 2 cycles. Cells were modified using a clinical grade retroviral vector containing the neomycin resistance gene, and were selected for using G418 after transduction. Grade 3 and 4 adverse events were observed in cohort 1, but were attributed to IL-2 administration. No serious adverse events were attributed to CIR administration. Persistence of modified cells was poor and did not exceed 3 weeks. This is likely a result of generation of antibodies to the infused T cells, as serum inhibitory factor that could be removed by incubation with protein G was found in patient serum post but not pre infusion. No effect on tumor, as measured by imaging and CA-125 antigen was observed in patients.

αCD19 redirected T cells with CD28-ζ signaling chain for CLL. Recently Brentjens, Sadelain, Riviere and colleagues initiated a clinical trial evaluating a chimeric immune receptor targeting CD19 and linked to the CD28 and CD3ζ signaling chains, for treatment of CLL. This is a two cohort study, with the first cohort receiving a low dose of cells to evaluate safety. The second cohort is designed to better evaluate potential efficacy, and the patients receive cytoreductive chemotherapy and a higher dose of cells. Cells are modified using a retroviral vector, and undergo rapid expansion using ClinExVivo beads from Invitrogen. To date, the treatment in cohort 1 has been well tolerated and resulted in transient anti-tumor effects in some patients. Results from this ongoing trial have not been published.

Lentiviral vector clinical experience. Considerable data shows that retroviral vectors are safe when expressed in human T cells; however, retroviral vectors appear less safe when used in human stem cells. Lentiviral vectors have the potential to be safer from the perspective of insertional mutagenesis, and they have substantially higher efficiency for genetically engineering human T cells. Therefore, we propose to use lentiviral vector technology to introduce the CART-19 T body constructs into the T cells. [REDACTED]

[REDACTED]

[REDACTED]

[figure not shown]
[figure not shown]
[figure not shown]
CD19 immunotoxin experience. Ideally, the target antigens for T body/CIR anti-tumor protocols should be carefully chosen, so as to be expressed only by malignant cells and not by normal cells. CD19 expression has been reported to be restricted to the B cell lineage, and thus the expectation is that toxicity from CART-19 T cells should be confined to the hematopoietic compartment. Most importantly, CD19 is not expressed on hematopoietic stem cells. Empiric clinical data with CD19 antibodies, radiolabeled CD19 antibodies and anti-CD19 immunotoxins supports this contention, as the infusions have not caused aplasia. Furthermore, the widespread clinical use of anti-CD20 (Rituximab), targeting CD20, an antigen with a distribution of expression similar to CD19, has shown an acceptable clinical toxicity profile that would be expected from B cell depletion. Recent clinical trials using chimeric immune receptors targeting CD20 and CD19 have also shown that redirected T cell immunotherapy appears safe for these targets.

Pheresis experience in young children. We have extensive experience over the past 15 years pheresing young children for therapeutic cells on our high-risk neuroblastoma trials (median age 3 years; studies including CHP-594, CHP-667, CCG A3973, COG ANBL00P1 and ANBL0532, various NANT studies), as well as a protocol for multiple cycle stem cell transplant in young patients with medulloblastoma (COG 99703). The effective lower limit for pheresis is 6 kg, and the effective lower limit for Medcomp catheter placement (as opposed to a femoral line) is 12 kg. Young children will be evaluated for suitability as a pheresis subject using our standard apheresis SOPs as approved by FACT.

#### **1.6 Inclusion of children in the research.**

Broadly speaking, we feel inclusion of pediatric patients in phase 1 or pilot protocols at the point where we have initial feasibility data from adult trials is appropriate. This is the approach that is generally pursued in early phase cancer trials for three reasons: i) to get clinical experience in pediatric populations, ii) to learn about issues with dosing or administration that might be specific to younger patients, and iii) allow pediatric access to novel therapies earlier in the development process. The population of pediatric relapsed/refractory leukemia and lymphoma patients targeted for enrollment in this study have no curative options for treatment. There is very little available on the horizon, especially for ALL patients, in terms of novel therapies at this stage of disease. New and highly innovative approaches are desperately needed for this group of pediatric patients. Our initial adult experience suggests a possible signal for efficacy. **With this, we believe there exists both compelling reasons to include children and the prospect of benefit in patients with no curative options.**

CONFIDENTIAL

### 1.7 Dose Rationale and Risk/Benefits

The primary objective of this protocol is to test the safety and feasibility of administering CART-19 cells to patients with advanced refractory hematologic malignancies. A secondary objective of this protocol is to determine which cytosolic signaling domain is superior for permitting CIR T cell engraftment and persistence. In this “competitive repopulation” scenario, we must administer a dose of cells that is 1) safe and 2) feasible to produce and can be tracked in the subject after infusion in order to determine if one T body construct is superior to the other. The basis for setting the starting dose was based on 1) Guidance for Industry: S6 Preclinical Safety Evaluation of Biotechnology-derived Pharmaceuticals; 2) Joint taskforce report from the BioIndustry Association (BIA) and the Association of the British Pharmaceutical Industry (ABPI) and 3) the available literature on phase I trials to date conducted with CIR T cells. The FDA guidance on safe starting dose (FDA Guidance for Industry: Estimating the Maximum Safe Starting Dose in Initial Clinical Trials for Therapeutics in Adult Healthy Volunteers) does not apply well for cell and gene therapy, and as such was not used to guide the selection of the starting dose for this study.

We believe that an initial i.v. dose of  $1.5 \times 10^7$ - $5 \times 10^9$  ( $0.3 \times 10^6$ - $1.0 \times 10^8$ /kg) CART-19 cells is optimal for this protocol. Because there are about  $1 \times 10^{12}$  T cells in a healthy adult (equivalent to  $2 \times 10^{10}$  T cells/kg), the proposed total (100%) dose is equivalent to about 0.5% of the total body mass of T cells. Therefore, we expect the initial frequency of cells to be present at about 0.5% at baseline following infusion. In addition, in our animal models, we find that a dose of 5 million cells per animal causes a robust antitumor response. The dose given to animals, when scaled, is similar to  $5 \times 10^9$  cells in humans. As an additional safety feature, the cells will be administered using an inpatient dose escalation approach (see section 6.6). The proposed dose in children is also consistent with or less than our prior T cell infusion trial in young children (CHP-667).

**Safety.** As described above in section 1.2, we propose to insert the scFv CIR constructs into T cells using lentiviral vector technology. At the University of Pennsylvania we have treated ■ patients using a related approach for patients with HIV infection with autologous T cells that contained a lentiviral vector. In the first protocol, each subject received a single i.v. infusion of  $1 \times 10^{10}$  lentiviral modified T cells; in the second protocol, each subject received up to 6 doses of  $0.5$ - $1 \times 10^{10}$  cells. The lentiviral engineered T cells were well tolerated in all patients, with follow up of up to 5 years. We have given doses of up to  $1 \times 10^{10}$  autologous *ex vivo* expanded T cells in several trials to patients with hematologic malignancies, HIV, and neuroblastoma and have found this to be well tolerated. The CART-19 cells may eventually be rejected by an immune response directed against the mouse scFv sequences. In summary, this dose was chosen because it is anticipated to be safe based on previous studies, and because it will permit sufficient engraftment in order to evaluate the primary and secondary endpoints of this study.

**Risk of tumor lysis related to cytoreductive chemotherapy.** The risk of tumor lysis syndrome (TLS) is dependent on the disease and burden of disease, but in most cases, this risk will be very low. Patients at highest risk for TLS have aggressive lymphomas (Burkitt’s or other ‘high grade’ NHL) and ALL. The risk of TLS in CLL, follicular lymphoma, mantle cell lymphoma and diffuse large cell lymphoma is thought to be low, but may be higher with highly effective therapy (Porter et al., NEJM 2011). Patients will be closely monitored both before and after chemotherapy and infusions including blood tests for potassium and uric acid. Patient-

CONFIDENTIAL

subjects will receive hydration and allopurinol to minimize any toxicity should significant acute tumor lysis occur.

Feasibility. The manufacturing feasibility is not expected to be an issue in this protocol, as given the combination of ex vivo cell culture and lentiviral vector technologies shown in figure 3, we expect to readily exceed the target dose of CART-19 cells that we have chosen.

Risk/benefits. Participation in this study will expose the patient to genetically engineered autologous T cells. The risk of the cells alone is low based on clinical experience. The unknown risk is that of the signaling domains in the CAR. T cell proliferation could be uncontrolled, however we have not observed this in our pre-clinical models. In this case, corticosteroids and chemotherapy would be given in an attempt to eradicate the CIR cells; this has worked in previous cases. It is possible the cells may be immunogenic, and that the patients will have an immune response directed against the scFv; this has not had clinical consequences in previous trials. If an immune response to the cells occurs, it is possible that the cells will be rejected. Three of 3 subjects developed HAMA and loss of T cell engraftment in the Lamers study, but zero of 7 patients in the Press study developed immune responses to their T bodies. It is possible that the CART-19 T cells will exert an anti-tumor effect; in a preliminary study, two patients treated with T bodies encoding an scFv specific for CD20 had a response that has lasted for a year.

Transient host B cell depletion is also a likely risk with CART-19 cells, since normal B cells express CD19. This is expected to resolve when the CART-19 cells are cleared.

## 2 STUDY OBJECTIVES

### Primary objectives:

1. Determine the safety and feasibility of administration of chimeric antigen receptor T cells transduced with the anti-CD19 lentiviral vector (referred to as “CART-19” cells), in patients who either:
  - a. have not received a prior allogeneic SCT or have 0% residual donor engraftment (“no allo” cohort), or
  - b. have relapsed after prior allogeneic SCT with any degree of residual donor engraftment (“allo” cohort).

In each case, the cells used will be collected from the subject, not from an allogeneic donor.

2. Determine duration of *in vivo* survival of CART-19 cells. RT-PCR analysis of whole blood will be used to detect and quantify survival of CART-19 TCR $\zeta$ :4-1BB and TCR $\zeta$  cells over time.

### Secondary objectives:

1. For patients with detectable disease, measure anti-tumor response due to CART-19 cell infusions.
2. To determine if the 4-1BB transgene is superior to the TCR $\zeta$  only transgene as measured by the relative engraftment levels of CART-19 TCR $\zeta$ :4-1BB and TCR $\zeta$  cells over time.
3. For patients with stored or accessible tumor cells (such as patients with active CLL, ALL, etc) determine tumor cell killing by CART-19 cells in vitro.

CONFIDENTIAL

4. Determine if cellular or humoral host immunity develops against the murine anti-CD19, and assess correlation with loss of detectable CART-19 (loss of engraftment).
5. Determine the relative subsets of CART-19 T cells (Tcm, Tem, and Treg)
6. Determine safety and efficacy in a test cohort of patients with CNS3 disease.

#### **Exploratory objectives:**

1. Determine if insufficient in vitro T-cell test expansion in response to CD3/CD28 costimulation is predictive of manufacturing or clinical outcome.

### **3 STUDY DESIGN**

#### **3.1 General Design**

We have designed a single-arm open-label phase I/IIa study to determine the safety, tolerability and engraftment potential of CART-19 T cells in patients with CD19+ hematologic malignancies. The general protocol schema is shown above in **figure 1** in section 1. All subjects will be dosed with CART-19 T cells. In all subjects treated to date, the CART-19 T cells contained only the TCR $\zeta$ :4-1BB transgene. A total of 72 subjects will be infused across “no allo”, “allo”, and CNS-3 cohorts. In order to infuse 72 patients, assuming a 20% drop out rate, we would enroll up to 86 patients.

A secondary objective is to determine if the 4-1BB transgene is superior to the TCR $\zeta$  only transgene. To test this, a cohort of 5 patients will be dosed with mixtures of TCR $\zeta$ :4-1BB and TCR $\zeta$  only cells, using a competitive repopulation strategy to determine the optimal signal transduction module in the chimeric receptor (**figure 13**). This cohort will proceed only after the 2 CARs to be compared are finalized. It is reasonable to assume that engineered T cells containing signaling domains that mimic physiologic signaling will function best in vivo, and therefore, we think that CART-19:TCR $\zeta$ :4-1BB will be superior to CART-19:TCR $\zeta$  only. **The null hypothesis is that they are equivalent.**

At entry, subjects will be staged and the suitability of their T cells for CART-19 manufacturing will be determined. Subjects in both the no allo and allo cohorts who have adequate T cells will be leukapheresed to obtain large numbers of peripheral blood mononuclear cells (PBMC) for CART-19 manufacturing. In each cohort, the subject is pheresed; however, in the allo cohort, T cells derived from donor engrafted cells may be collected from the subject. The T cells will be purified from the PBMC, transduced with CART-19 lentiviral vector, expanded in vitro and then frozen for future administration. Chemotherapy will then be given. Following tumor burden reassessment, CART-19 cells will be thawed and infused.

Subjects will have blood tests to assess safety, and engraftment and persistence of the CART-19 cells at regular intervals through week 4 of the study (see table in Appendix 2). The subsets of circulating T-cells that contain the CART-19:TCR $\zeta$ :4-1BB and CART-19:TCR $\zeta$  only lentiviral vector will be assessed at various times after infusion and compared to the baseline sample. Following the 6 months of intensive follow-up, subjects will be evaluated quarterly for two years with a medical history, a physical examination, and blood tests. Following completion of the primary follow-up phase, subjects will continue to be followed for disease-free survival (as applicable) and overall survival every 3 months until they withdraw consent or until two years post the last subject infusion, as part of Secondary Follow-up. Subjects will also be asked

CONFIDENTIAL

to enroll in a 15 year long-term follow-up protocol to evaluate specific long-term adverse events related to the study product.

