Observation and monitoring of patients will continue on a monthly basis until 24 weeks after a cell infusion is given. In subjects given a mixture of CART-19 cells, the change in the ratio of the vector transduced cells to each other between baseline and week four will be evaluated. After two years, annual follow-up for lentiviral vector safety will be carried out under a separate destination protocol for 15 years post infusion in accordance with FDA guidelines for retroviral vectors.

72 subjects will be targeted for infusion in this study. We have observed a drop out rate of less than 20% or less due to disease progression or clinical deterioration between enrollment and initial infusion (this will take about 6-8 weeks for screening-apheresis to dosing). However, as we are eliminating the test expansion, we may increase this dropout rate by 5-15%. Thus, up to 86 subjects will be initially enrolled to allow our goal of 72 infusions.

All safety data after initial CART-19 infusion will be summarized regardless of whether patient receives subsequent CART-19 infusions or not (Section 6.6). Efficacy data will be summarized from initial CART-19 infusion to first documented relapse or end of follow-up, whichever occurs first. Additional analyses may be planned as needed.

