### 7.3 Sample Size

This is a 86 patient phase I/IIa study with an anticipated dropout rate of 20%. If this exploratory study suggests that one vector persists and engrafts better than the other vector, then a larger follow-on trial will be designed that has the statistical power to assess the potential efficacy of that vector.

CONFIDENTIAL

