#### 7.4 Safety

This trial will infuse up to 72 patients. This may require enrollment of more subjects because of the dropout rate. In order to assess the confidence with which we can obtain an initial estimate on the toxicity rate in each cohort, the table below presents the exact 95% confidence intervals for the toxicity rate based on the first 7 or 10 subjects

n=7 Evaluable Subjects		n=10 Evaluable Subjects	
Observed Toxicity Rate	95% Exact Confidence Interval	Observed Toxicity Rate	95% Exact Confidence Interval
0% (0/7)	(0%, 41%)	0% (0/10)	(0%, 31%)
14% (1/7)	(0%, 58%)	10% (1/10)	(0%, 45%)
29% (2/7)	(4%, 71%)	20% (2/10)	(3%, 56%)
43% (3/7)	(10%, 82%)	30% (3/10)	(7%, 65%)

With 10 subjects and a true underlying toxicity rate of 20%, the probability of failing to observe an adverse event is 11%. The probability decreases to 3% if the true toxicity rate is 30%. Taking into account potential drop out due to disease progression either prior to infusion or before the planned response assessment is possible, with seven subjects the probability of failing to observe an adverse event is 21%, if the true toxicity rate is 20% and decreases to 8% if the true toxicity rate is 30%.

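### 72 infused, 86 enrolled and 20% drop-out do not agree: at 20%, 86 enrolled gives about 69 infused, and 72 infused needs 90 enrolled

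*Combined protocol and SAP*

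**What the plan says.** All references are to the combined protocol and SAP.

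- **Study Summary:** 72 subjects infused, with 86 as the upper limit on enrolment.
- **Section 3.1:** "A total of 72 subjects will be infused across" the three cohorts. The enrolment number is then derived: "In order to infuse 72 patients, assuming a 20% drop out rate, we would enroll up to 86 patients".
- **Section 7.1:** "72 subjects will be targeted for infusion in this study". Past experience is a "drop out rate of less than 20% or less due to disease progression or clinical deterioration between enrollment and initial infusion". A possible increase follows: "as we are eliminating the test expansion, we may increase this dropout rate by 5-15" per cent. The conclusion is: "Thus, up to 86 subjects will be initially enrolled to allow our goal of 72 infusions".
- **Section 7.3:** "This is a 86 patient phase I/IIa study with an anticipated dropout rate of 20" per cent.
- **Section 7.4:** "This trial will infuse up to 72 patients". The next sentence allows that extra subjects may have to be enrolled because of drop-out, but gives no number.

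**The concern.** Section 7.1 places drop-out between enrolment and first infusion. The people at risk of it are therefore those enrolled, and a 20% rate is naturally a share of that group. Section 7.3 reads the same way, since it attaches the 20% to a study of 86. On this base, 86 is not the number that delivers 72 at 20% loss. It looks as if 20% was added to 72, when 72 should have been divided by 0.80.

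Section 7.1 makes this harder to follow. It says that dropping the test expansion may raise drop-out by 5-15%, and then concludes with the same 86. It does not say whether the increase is relative or in percentage points, or whether the 20% already includes it.

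What is at stake is mainly clarity. At the planned rate, 72 infused and a ceiling of 86 enrolled cannot both be expected to hold, and the plan does not say which gives way. Two other sections depend on these numbers. Section 7.6 treats enrolled versus infused as a measure of feasibility, which is part of the first primary objective. Section 8.5 makes departures that affect sample size reportable to the Regulatory Sponsor.

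**Working it through.** **Inputs.** Target infused: 72 (Study Summary; sections 3.1 and 7.1). Enrolled: 86 (Study Summary; sections 3.1, 7.1 and 7.3). Drop-out: 20% (sections 3.1 and 7.3). Possible increase: 5-15% (section 7.1).

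**1. Reproducing the plan's 86.**
- Rate applied to those infused, N × (1 + d): 72 × 1.20 = 86.4. This gives 86 when rounded down.
- Rate applied to those enrolled, N / (1 − d): 72 / 0.80 = 90. This does not give 86; the difference is 90 − 86 = 4.

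**2. Expected number infused from 86 at 20%.** 86 × 0.80 = 68.8, about 69. The shortfall is 72 − 68.8 = 3.2.

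**3. Drop-out rate that 86 does cover.** (86 − 72) / 86 = 14/86 = 16.3%. At 16%, 86 × 0.84 = 72.2 infused; at 17%, 86 × 0.83 = 71.4.

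**4. Chance of reaching 72.** Assume that each enrolled subject is infused independently with probability 0.80. The binomial probability of at least 72 infused is then about 24% from 86 enrolled and about 56% from 90.

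**5. Effect of the 5-15% increase, if it comes on top of 20%.** The plan does not say how to read it, so both readings are shown. Enrolment is rounded up.

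| Reading | Drop-out | Enrolled needed for 72 | Infused from 86 |
|---|---|---|---|
| Relative, +5% | 21% | 72 / 0.79 = 91.1, so 92 | 67.9 |
| Relative, +15% | 23% | 72 / 0.77 = 93.5, so 94 | 66.2 |
| Points, +5 | 25% | 72 / 0.75 = 96 | 64.5 |
| Points, +15 | 35% | 72 / 0.65 = 110.8, so 111 | 55.9 |

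If the 20% already includes the increase, steps 1 to 4 apply unchanged.

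**6. Effect on precision.** No planned calculation uses 72: section 7.4 works with 7 and 10 subjects, and section 7.5 with 20 and 7. As an illustration, the upper two-sided exact 95% limit with zero events is 1 − 0.025^(1/n). It is 5.2% at n = 69 and 5.0% at n = 72.

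**The case against.** The strongest reply is that 86 may be enough in practice. Section 7.1 gives 20% as an upper bound on what has been seen, and 16.3% lies below that bound. This stands as a possibility. It does not rescue the derivation, because sections 3.1 and 7.3 plan on 20% itself, section 7.1 expects a rise, and no lower rate is stated anywhere.

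A second reply is that the base of the 20% is inferred. No section says that it is a share of those enrolled, section 7.3 does not define its rate, and section 7.4 also mentions loss after infusion, before the response assessment. So 86 could be read as a 20% over-enrolment allowance. The inference remains the natural one: section 3.1 calls the figure a drop-out rate, and section 7.1 ties drop-out to the interval before first infusion.

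A third reply is that 72 is clearly the goal and enrolment the flexible quantity. Section 7.1 speaks of a goal, the heading of section 5.3.1 numbers infused patients 1 to 72, and section 7.4 foresees extra enrolment. That is a fair reading of the intent. But the Study Summary, section 3.1 and section 7.1 all word 86 as a ceiling, and no section says how far enrolment may go beyond it.

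Finally, the consequences are small, and any shortfall would show in the enrolled-versus-infused report of section 7.6. This is correct, and it limits the weight of the point. The varied wording for 72 (fixed total, target, maximum) is editorial.

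**Conclusion.** The concern holds, as a minor one. With 20% taken as a share of those enrolled, the plan's three numbers are inconsistent: 86 enrolled gives about 69 infused, roughly 3 short, and 72 infused needs 90 enrolled, 4 above the stated ceiling. The three numbers agree only if 20% is taken of those infused, which does not fit section 7.1's account of drop-out. On average, 86 is enough only at a drop-out rate of 16.3% or less.

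The 5-15% increase is unresolved. If it is additional to 20%, the gap widens by an amount that depends on how it is read. No test, power statement, precision table or analysis changes.

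**What to change.** In the Study Summary and sections 3.1, 7.1 and 7.3, choose one of these:

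1. Keep 86 as the enrolment ceiling and state that about 69 infusions are expected at 20% drop-out.
2. If 72 infused is binding, restate enrolment as 90 at 20%.
3. If the observed data support it, state that 86 assumes drop-out of about 16%. This is the weakest choice while section 7.1 expects drop-out to rise, and it needs the observed rate to be given.

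In section 7.1, give the planning rate and say that its base is those enrolled. State whether the 5-15% is relative or in percentage points and whether the planning rate includes it, and give the matching number enrolled or infused.

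Use one description of 72 throughout, and align the ceiling of 86 with the section 7.4 sentence on enrolling further subjects.

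The cost is wording and one recomputed number. Choices 1 and 3 add no patients. Choice 2 raises the enrolment figure by 4, or by more if a planning rate above 20% is adopted. No analysis changes.
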